## 8.2 Analysis

The study is an exploratory study.

Definition of vitamin D status:

Nmol/L	Ng/mL	Health status	Vitamin D status
< 30	< 12	Associated with vitamin D deficiency, leading to rickets in infants and children and osteomalacia in adults	Deficiency
30-50	12-20	Generally considered inadequate for bone and overall health in healthy individuals	Insufficiency
≥ 50	≥ 20	Generally considered adequate for bone and overall health in healthy individuals	Adequacy
> 125	> 50	Emerging evidence links potential adverse effects to such high levels, particularly > 150 nmol/L (>60 ng/mL)	Toxicity

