## 1. Study Synopsis

Title of clinical trial	Omega 3 and Vitamin D dosage in a population with moderate to high risk of AMD
Protocol Short Title/Acronym	OVID-AMD
Sponsor name	UZ Leuven
Principal Investigator	[name]
Medical condition or disease under investigation	AMD
Purpose of clinical trial	Blood serum dosage of omega 3 and vitamin D in individuals with moderate and high risk of AMD as determined by STARS scores of $\geq 10$
Primary objective	To detect individuals at high and moderate risk of AMD in the Belgium population and to perform a blood serum dosage of omega 3 and Vitamin D
Secondary objective (s)	Dosage of zinc oxide and cupric oxide
Trial Design	Multi-centric, epidemiological and interventional survey

Endpoints	Blood dosage of omega 3 and Vitamin D, zinc oxide and cupric oxide
Sample Size	Not applicable
Summary of eligibility criteria	
 
- subjects <math>\geq</math> 55 years
 
- subjects with family history of AMD
 
- age-related maculopathy present
 
- no previous intake of eye nutritional supplements < 4 months prior to enrollment
 
- no current intake of multivitamins especially when containing Vit D
 

Maximum duration of treatment of a Subject	1 visit
Version and date of final protocol	
Version and date of protocol amendments	

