### 8. Statistics

#### 8.1 Sample size

We anticipate to include 50 subjects to this pilot study. There is no control group and it is an exploratory study, so no power calculation has been done. The study results will provide us trends to build a bigger study.

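### Do the overlapping vitamin D status limits in Section 8.2 need to be rewritten?

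*Combined protocol and SAP*

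**What the plan says.** Section 8.2 calls the study exploratory and then gives a table headed "Definition of vitamin D status". In nmol/L (ng/mL) its rows are:

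- Deficiency: < 30 (< 12)
- Insufficiency: 30-50 (12-20), described as "Generally considered inadequate for bone and overall health in healthy individuals"
- Adequacy: ≥ 50 (≥ 20), described as "Generally considered adequate for bone and overall health in healthy individuals"
- Toxicity: > 125 (> 50), where the text begins "Emerging evidence links potential adverse effects to such high levels"

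Nothing else in Section 8.2 tells the analyst what to do with the classes. The Synopsis gives the primary objective as finding people at moderate or high risk of AMD and "to perform a blood serum dosage of omega 3 and Vitamin D"; its Endpoints entry lists the blood measurements themselves. Section 8.1 states: "We anticipate to include 50 subjects to this pilot study". It adds that the study is exploratory and has no control group, "so no power calculation has been done".

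**The concern.** A set of status classes should give each subject one class. These rows, taken as printed, do not. The value 50 nmol/L closes the Insufficiency range and opens Adequacy, and Adequacy has no upper limit, so it contains all of Toxicity. No precedence rule is stated. Two units are printed and neither is named as the one that classifies a subject.

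Vitamin D is one of the two analytes in the primary objective, and this table is the only concrete content of the analysis section. If results were tabulated by status on the literal limits, the class counts could sum to more than the number of subjects. The share called inadequate would also depend on who handled the boundary, at the point where the table's description turns from inadequate to adequate.

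**Working it through.** **Inputs.** The limits come from the Section 8.2 table and N = 50 from Section 8.1. There is no power calculation to reproduce. The documents give no expected mean, SD, assay or reporting precision.

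**1. Where the overlaps lie.** The four rows were applied literally to every value from 0 to 250 nmol/L in steps of 0.1.

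- At or below 125 nmol/L, the only value with two classes is 50.0.
- Every value above 125 has two classes (Adequacy and Toxicity); 125 itself is Adequacy only.
- There are no gaps, and 30 is Insufficiency only.

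**2. Whether the units disagree.** 30/12 = 50/20 = 125/50 = 150/60 = 2.5. The two columns describe the same cut-offs, so the choice of unit can matter only through rounding.

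**3. Whether the table supplies its own answer.** The first row is < 30, so 30 belongs to the class above it. The third row is ≥ 50, so by its explicit sign 50 also belongs to the class above. The second row is a bare range with no sign. The last row is a separate class that starts above 125. The ordinary reading is therefore < 30; 30 to < 50; 50 to 125; > 125. Under it, every value from 0 to 250 nmol/L has exactly one class and the counts sum to 50.

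**4. How many subjects could be affected.** Assume concentrations are normal with mean 40-70 and SD 15-25 nmol/L. The expected number on the boundary is 50 × P(reported value is exactly 50 nmol/L or 20 ng/mL).

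| Assumed reporting | Interval read as the cut-off (nmol/L) | Probability | Expected of 50 |
|---|---|---|---|
| 0.1 nmol/L | 49.95-50.05 | 0.0011-0.0027 | 0.05-0.13 |
| 0.1 ng/mL | 49.875-50.125 | 0.0027-0.0066 | 0.14-0.33 |
| whole nmol/L | 49.5-50.5 | 0.0109-0.0266 | 0.5-1.3 |
| whole ng/mL | 48.75-51.25 | 0.0274-0.0664 | 1.4-3.3 |

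The finest and coarsest intervals differ in width by 2.5/0.1 = 25, so the answer varies about 25-fold with an assumption the documents do not settle.

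For the upper overlap, P(> 125) = 0 to 0.0139, which is 0 to 0.7 subjects.

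The effect of unit is similar in size. A value from 48.75 to < 50 nmol/L is Insufficiency in nmol/L but reads 20 after rounding to whole ng/mL. P = 0.013-0.033, or 0.6-1.7 of 50.

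**5. Scale.** Each subject moves a percentage by 1/50 = 2 points. The largest boundary shift is 0.0664, or 6.6 points. It needs whole ng/mL reporting and a mean of 50 with SD 15. The 95% half-width for a 50% proportion at N = 50 is 1.96 × √(0.25/50) = 0.139, or 14 points, so the extreme case is about half the sampling error.

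**The case for a change.** The best case for a change is that the overlap is plainly in the current text, identical in both unit columns, and cheap to remove. Boundary values need not be rare. With results in whole ng/mL, the same model puts the chance that at least one of 50 subjects sits on the boundary at 0.75-0.97, and with whole nmol/L at 0.42-0.74. The study is multi-centric, so different people could classify differently. Section 8.1 also expects the results to inform a larger study, into which an unclear class share could be carried.

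The observation about the text stands, as does the absence of a precedence rule. The claim of harm does not:

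- It supposes a table of class counts that the plan does not call for, built by an analyst who enters one subject twice.
- The natural repair follows the table's own inequality signs, so it only writes down the reading already available.
- A larger study would draw on the measured concentrations, which can be re-cut at any threshold.
- At one-decimal reporting in nmol/L, the chance of even one boundary value falls to 0.05-0.12.

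The Toxicity label adds nothing. Its row text covers the high levels in that row and stresses those above 150 nmol/L, which does not conflict with a cut-off of 125.

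**Conclusion.** No change to the plan follows. The limits touch at 50 nmol/L (20 ng/mL), and Adequacy lacks a printed upper bound, but this is imprecise notation with an evident reading. No endpoint, test, sample size or conclusion depends on it. The number of subjects affected cannot be determined from the documents. Under the assumed normal range it is well under one of 50 with one-decimal reporting, and at most a few with whole ng/mL. Those figures rest wholly on the assumed mean, SD and rounding. The conclusion does not: it rests on the endpoint being the measured level and on the plan specifying no analysis by class.

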## 9. Quality assurance

Give details as to how QA will be maintained, mention SOP's if available

## 10. Direct access to source data and documents

Dr. [name], [name]. [name] , Dr. [name] and the institutions will permit trial-related monitoring, audits, EC review, and regulatory inspections (where appropriate) by providing direct access to source data and other documents (ie subjects' case sheets, blood test reports, X-ray reports, histology reports etc).

## 11. Ethics and regulatory approvals

The trial will be conducted in compliance with the principles of the Declaration of Helsinki (current version), the principles of GCP and in accordance with all applicable regulatory requirements. This protocol and related documents will be submitted for review to Ethics Committee of UZ Leuven.

The Study can and will be conducted only on the basis of prior informed consent by the Subjects, or their legal representatives, to participate in the Study. The Participating Site shall obtain a signed informed consent form (ICF) for all subjects prior to their enrollment and participation in the Study in compliance with all applicable laws, regulations and the approval of the (local) Ethics Committee, if required. The Participating Site shall retain such ICFs in accordance with the requirements of all applicable regulatory agencies and laws.

The Investigator and the Participating Site shall treat all information and data relating to the Study disclosed to Participating Site and/or Investigator in this Study as confidential and shall not disclose such information to any third parties or use such information for any purpose other than the performance of the Study. The collection, processing and disclosure of personal data, such as patient health and medical information is subject to compliance with applicable personal data protection and the processing of personal data (Directive 95/46/EC and Belgian law of December 8, 1992 on the Protection of the Privacy in relation to the Processing of Personal Data)

Data are **anonymous** if no one, not even the researcher, can connect the data to the individual who provided it. No identifying information is collected from the individual.

When data are **coded**, there continues to be a link between the data and the individual who provided it. The research team is obligated to protect the data from disclosure outside the research according to the terms of the research protocol and the informed consent document. The subject's name or other identifiers should be stored separately from their research data and replaced with a unique code to create a new identity for the subject. Note that coded data are not anonymous.

## **12. Data Handling**

Electronic patient file

## **13. Data Management**

Electronic patient file

Paper CRF to collect questionnaires

## **14. Translational research**

Blood sample will be taken.

## **15. Publication Policy**

E.g in case of multicentre trial:

It is anticipated that the results of the overall Study shall be published in a multi-centre publication, involving the data of all clinical sites participating in the Study.

Participating Site is not allowed to publish any data or results from the Study prior to the multicentre publication, provided however that Participating Site is allowed to publish the results generated at the Participating Site if the multicentre publication has not occurred after 12 months from Study database lock.

Any publication by Participating Site will be submitted to the Sponsor for review at least thirty (30) days prior to submission or disclosure. Sponsor shall have the right to delay the projected publication for a period of up to three (3) months from the date of first submission to the Sponsor in order to enable the Sponsor to take steps to protect its intellectual property rights and know-how.

Publications will be coordinated by the Investigator of Sponsor. Authorship to publications will be determined in accordance with the requirements published by the International Committee of Medical Journal Editors and in accordance with the requirements of the respective medical journal.

## **16. Insurance/Indemnity**

In accordance with the Belgian Law relating to experiments on human persons dated May 7, 2004, Sponsor shall assume, even without fault, the responsibility of any damages incurred by a Study Patient and linked directly or indirectly to the participation to the Study, and shall provide compensation therefore through its insurance.”

## **17. Financial Aspects**

Thea Pharma allows a subsidy of 15000€

